Statistical Analysis Plan

NCT05740098

April 1, 2023

Statistical Analysis Plan

Condition Assignment/Randomization

The study consists of a baseline assessment, 12 weeks of exposure to the treatment conditions, and follow-up visits at 24 and 48 weeks following their quit dates. Participants will be randomly assigned to one of the three study conditions (Best Practices [BP], Best Practices plus Financial Incentives [BP+FI], Best Practices plus Financial Incentives plus Nicotine Replacement Therapy [BP+FI+NRT]), with randomization conducted using a covariate-adaptive randomization scheme. Covariates considered in the randomization scheme include the age of the child who will participate in the trial with Mother (< 6 years of age versus 6-11 years of age), number of cigarettes/day (CPD) smoked by the mother (≤ 20 CPD versus > 20 CPD), mother's level of education (< high school versus high school diploma or higher), maternal use of e-cigarettes (yes versus no), number of smokers in the home (mother only versus at least one other smoker), type of insurance (Medicaid versus private insurance) and recruitment site. Randomization was conducted separately for mothers based on the presence or absence of opioid use disorder (OUD).

Sample Size

Sample size was determined based on having sufficient power to detect differences between treatment conditions corresponding to our first specific aim on point prevalence abstinence differences at the 12-week end-of-treatment assessment and the 24-week follow-up assessment. Our completed trials on smoking cessation among pregnant women provide relevant information for estimating sample size for the proposed study (Higgins et al., 2022). Across three trials, biochemically-verified, 7-day point-prevalence abstinence in the contingent and non-contingent incentive conditions at the end-of-pregnancy were 35% in the contingent conditions and ranged from 9-23% in the non-contingent control conditions. We estimate that the BP+FI and BP+FI+NRT conditions will produce $\geq 35\%$ abstinence rates and the BP condition will produce 15% abstinence rates. The proposed trial sample size of 240 trial participants (80/condition) will result in estimated power of 0.95 using alpha = 0.05 for detecting differences among the treatment conditions (i.e., 40% vs. 15%) at 12-week end-of-treatment assessment. Power is estimated to be 0.80 to detect a 15% (i.e., 20% vs. 5%) difference between treatment conditions at the 24-week follow-up assessment. For the second specific aim relating to the objective measure of secondhand smoke exposure (SHSe) in children, power is estimated to be 0.80 using alpha = 0.05 to detect treatment differences of approximately 35% with respect to the mean decrease in urine cotinine levels from baseline and > 0.80 in comparisons by maternal smoking status. This computation is based on variability estimates from Hovell et al. (2009) which corresponds to a log transformed analysis and geometric means. This assumes moderate correlation ($r = 0.50$) between cotinine levels within subjects across assessment times. If our average baseline levels are similar to theirs, this relative difference translates to an absolute mean difference of approximately 4.2 ng/ml between treatment conditions and larger effects in comparisons by maternal smoking status. For the logistic regression analyses corresponding to the secondary aim on behavioral economic predictors, power is estimated to be 0.80 using alpha = 0.05 for detecting explanatory variables that have odds ratios ranging from 2.0 to 2.5 per one

SD change from their mean assuming total model R^2 ranging from 0.20 to 0.40. This exact estimate is dependent on the total number of predictors and the overall R^2 of the model with lower detectable OR's associated with smaller overall R^2 .

Study Populations

Intention-to-Treat Population

Participants will be randomized to study conditions after the completion of the intake assessment. For data analyses, the full analysis population will include participants completing the randomization process, which included successfully completing the intake assessment and being randomized to a treatment condition. Participants will be analyzed based upon the condition to which they were assigned, regardless of protocol violations and/or compliance to condition assignment. Our primary results will be based on this intention-to-treat population (i.e., randomized to a condition and received the specified treatment) (Armitage, 1983). Participants missing assessment visits and/or lost-to-follow-up will be assumed to be smokers for these analyses.

Statistical Analysis

Baseline Characteristics

Baseline characteristics will be summarized by treatment condition (BP, BP+FI, BP+FI+NRT) to identify any group imbalances post-randomization. Continuous variables will be summarized by mean and standard deviation and compared by one-way ANOVA, with variable transformations conducted as necessary to improve the normality of the distributions. Categorical variables will be summarized by frequencies and percentages and compared using the Chi-square test.

Primary Endpoint Analysis

The primary endpoints are maternal 7-day point-prevalence smoking abstinence at the 12- and 24-week assessments. Comparison of point-prevalence abstinence among treatment conditions across all periodic assessments will be analyzed using a mixed model repeated measures for categorical data based on generalized estimating equations utilizing a logistic link function (SAS PROC GENMOD, SAS Institute, Cary, NC). Covariates of interest that will be identified, based on characteristics that differ significantly across study conditions and are predictive of outcome, will be included in the model. Data analysis for child SHSe will be based on child urine cotinine levels, assessed at 6-, 12-, 24-, and 48-week assessments. Comparison of treatment conditions will use a mixed-model repeated-measures analysis (SAS PROC MIXED, SAS Institute, Cary, NC), with baseline urine cotinine levels included as a covariate. As noted for the point-prevalence abstinence rates, covariates of interest will be identified based on characteristics that differ significantly across study conditions and are predictive of outcome. In addition, models will include potential confounders (Collins et al., 2020). Analysis of variance will be used to compare SHSe levels by maternal smoking status at the follow-up assessments, controlling for baseline levels. Additional covariates include those characteristics included in the prior analyses.

Secondary Endpoint Analysis

Group comparisons on continuous abstinence from quit date to 24-week assessments will be assessed using a 3x2 contingency table with a Chi-square test. A significant overall Chi-square test will be followed with pairwise tests. Logistic regression will be used to examine the association between baseline temporal discounting, measured by the Kirby delay discounting task, and other measures of price sensitivity, measured by the Cigarette Purchase Task (CPT), with subsequent abstinence at follow-up assessments (6-, 12-, 24- and 48-week assessments). Baseline delayed discounting will be expressed as the logarithm of each participant's estimated parameter k. Measures from the CPT will be transformed as necessary. Models will include treatment condition and the interaction of treatment condition with k or the CPT measures.

Missing Data

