children's health (Halterman et al., 2010), including smoking parents (Johansson et al., 2005). A report by Mahabee-Gittens (2002) also provides insight into the smoking-cessation intentions of parents with young children. In this study of 102 disadvantaged parents, 82% had intentions to quit but only 21% actually made a quit attempt. Importantly, 66% reported that they would be interested in joining a smoking- cessation program and/or trying a smoking-cessation medication. Despite knowledge of the adverse consequences of continued smoking and intentions to quit, why don't these mothers stop smoking?

Behavioral economics offers potential answers to that question. Results from several studies demonstrate that smokers discount the value of delayed reinforcement more than nonsmokers, a phenomenon known as delay discounting (DD) (Bickel et al., 2007). This difference can be summarized as smokers showing a greater preference for more immediate, smaller magnitude rewards (e.g., smoking a cigarette) over more delayed, larger-magnitude rewards (e.g., a healthy child). Moreover, other studies have shown that individuals with less education discount more than those with more education (e.g., de Wit et al., 2007). Additionally, two studies by our group have demonstrated that greater discounting predicts poorer treatment outcomes in pregnant smokers (Washio et al., 2011; Yoon et al., 2007). Yoon et al. (2007) demonstrated that among women who quit smoking during pregnancy (N=48), those who discounted more at baseline were also more likely to relapse back to smoking by 6-months postpartum. Using data from our research clinic for cocaine abusers, Washio et al. (2011) demonstrated that DD of hypothetical monetary reinforcers predicted the amount of abstinence achieved among 36 outpatients receiving incentives with relatively low- or high-magnitude monetary value. DD predicted the number of weeks of cocaine abstinence, adjusting for treatment condition ($p = .02$). Interestingly, greater discounters achieved less abstinence in the low-magnitude ($p = .02$), but not in the high-magnitude ($p = .30$) incentive conditions, suggesting that the high-magnitude incentives were helping individuals abstain despite their steeper discounting.

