Other behavioral-economic tasks also have important potential contributions to make toward understanding persistent smoking among disadvantaged populations and individual differences in response to incentives and other interventions. One instrument that we are proposing to examine in this application uses a simulated cigarette purchase task (CPT) to generate demand curves for smoking-produced reinforcement (e.g., Murphy et al., 2011). Individuals report the number of cigarettes they would smoke in a hypothetical day across a range of prices per cigarette. In approximately 20 min, the task generates a rich array of measures of demand and price sensitivity, including breakpoint, and intensity and elasticity of demand among others. The same task has been used effectively to assess individual price sensitivity with alcohol and opioid consumption (Jacobs & Bickel, 1999; Murphy et al., 2009), differences between smokers with vs. without serious mental illness (MacKillop & Tidey, 2011), and has been shown to predict treatment outcome in problem drinkers (MacKillop & Murphy, 2007).

Incentives can be conceptualized as altering the price of smoking by adding the opportunity cost of forfeiting the incentive available for abstinence to the price of purchasing the cigarettes. As such, there is a sound theoretical rationale to anticipate that individual differences in elasticity of demand (i.e., sensitivity to price) may predict sensitivity to the incentives, with successful treatment response corresponding to greater price sensitivity. Similarly, NRT can be conceptualized as substituting an inferior form of nicotine reinforcement for cigarette smoking. As such, there is a sound theoretical rationale for anticipating that individuals who are already more sensitive to price in the absence of the inferior substitute (at baseline) may show even greater elasticity of demand when NRT is available to substitute for smoking. That is, they would be expected to benefit more from the combined incentives + NRT intervention than those with more inelastic baseline demand curves. We will explore such relationships in the proposed study and believe that doing so has the potential to enhance understanding of the processes underpinning successful treatment with these and other interventions, individual differences in treatment response, differences between treatment conditions, and provide future targets for improving interventions with disadvantaged smokers.

Summary

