Primary aim # 2: determine whether maternal smoking cessation decreases objective measures of SHSe in children. Urine samples will be collected from the youngest child of each maternal participant at each follow-up assessment for determination of cotinine levels. We will examine this outcome by (a) comparing between treatment conditions and (b) comparing children of abstainers versus smokers independent of treatment condition. We hypothesize that (a) both incentives interventions will decrease child cotinine levels significantly more than usual care alone and (b) that SHSe levels will be significantly lower among children of abstainers than smokers.

Secondary aim: utilize behavioral-economic measures to improve understanding of treatment process and predict outcomes. Women will complete smoking-price sensitivity and delay-discounting tasks at study intake and follow-up assessments. We hypothesize that cigarette price sensitivity will increase as an orderly function of treatment intensity and differ between treatment conditions, and that steeper baseline discounting (i.e., greater impulsivity) will predict smoking abstinence at follow- up assessments after controlling for the influence of treatment.

METHODS AND PROCEDURES

Study Design: Describe the research design, including a description of any new methodology and its advantage over existing methodologies.

This study is a randomized clinical trial with three treatment conditions. Treatment conditions will last for 12 weeks and consist of either **A**: usual care for reducing SHSe. **B**: provisions of incentives contingent upon biochemically-verified maternal smoking abstinence or **C**: the incentive program combined with provision of and support in using of pharmacotherapies. Outcome measures will include maternal abstinence rates, child cotinine exposure and the interaction of behavioral economic measures and treatment success. This extended treatment period of combined incentive and pharmacotherapy support represents a novel and intense approach to reducing smoking and second-hand smoke exposure in these vulnerable populations.

Procedures: Describe all procedures (sequentially) to which human participants will be subjected. Identify all procedures that are considered experimental and/or procedures performed exclusively for research purposes. Describe the types, frequency and duration of tests, study visits, interviews, questionnaires, etc.

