Treatment conditions will be compared for differences in baseline characteristics using t-tests for continuous measures and chi-square tests for categorical variables. If specific characteristics differ significantly across treatment conditions and are predictive of treatment outcomes, they will be considered as potential covariates in subsequent analyses. Primary analyses will include all subjects randomized to treatment conditions independent of early dropout, noncompliance, etc., consistent with an intent-to-treat approach to randomized clinical trials (Armitage, 1983). The primary outcome measures in this trial will be point prevalence smoking abstinence at the 12- and 24-week assessments. We will analyze abstinence at 48 weeks for an estimate of relapse rates and for use in comparing SHSe levels and secondhand smoke-related illness rates in children of abstainers and smokers but are not developing this initial trial with those at assessments as a primary outcome. We will also assess continuous abstinence from the quit date through 24-week assessment. Abstinence will be defined as a self-report of no smoking in the past 7 days, breath CO < 6 ppm, confirmed by urine cotinine testing (< 50 ng/ml) of specimens collected at the 12- and 24-week assessments by an independent laboratory. The study is designed to have sufficient power to have a greater than 80% chance of detecting treatment difference at each assessment point through 24-weeks. Abstinence rates at each assessment will be compared across the treatment conditions using chi square tests or Fisher's Exact tests, if small expected cell frequencies are present. Comparison of point-prevalence abstinence rates among treatment conditions across all periodic assessments will be analyzed using mixed model repeated measures for categorical data based on generalized estimating equations utilizing a logistic link function (SAS: PROC GENMOD, SAS Institute, Cary, NC) with assessment time, treatment condition, and their interaction as factors. Treatment comparisons and temporal changes in children's mean urine cotinine will be examined using repeated measures analysis of variance (PROC MIXED) across assessments. Group comparisons at each time point will be based on Fisher's protected LSD. Because cotinine levels are typically skewed, data will be log transformed prior to analyses. Analysis of variance will be used to compare SHSe levels by maternal smoking status at specific follow-up assessments. Logistic regression will be used to examine the association between baseline temporal discounting and other measures of price sensitivity and subsequent abstinence. Baseline DD will be expressed as the logarithm of each participant's estimated parameter k, and elasticity of demand in the models from the cigarette purchase task. Additional explanatory variables in the models will include treatment condition and subject demographic and smoking characteristics. Additional models will examine potential interactions between treatment condition and measures from the demand curves as well as target child characteristics such as baseline cotinine level.

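### The SAP's discounting and cigarette-demand models carry over none of the demographic and smoking covariates that the protocol puts in them, so an association with abstinence cannot be read as treatment process.

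*SAP*

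**What the plan says.** The secondary aim (protocol, Objectives) is to use behavioral-economic measures both to understand treatment process and to predict outcome. The two documents specify its logistic models differently.

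- Protocol, Statistical Considerations: log k and the demand measures are entered, and "Additional explanatory variables in the models will include treatment condition and subject demographic and smoking characteristics". Interactions come separately: "Additional models will examine potential interactions between treatment condition and measures from the demand curves".
- SAP, Secondary Endpoint Analysis: "Models will include treatment condition and the interaction of treatment condition with k or the CPT measures". No demographic or smoking variable is named, and the change is not explained.

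The SAP does have a covariate rule: "Covariates of interest that will be identified, based on characteristics that differ significantly across study conditions and are predictive of outcome". That rule, and the references to confounders and to previously selected covariates, all stand under Primary Endpoint Analysis. They are attached to the abstinence model, the child cotinine model and the comparison of child exposure by maternal smoking status. Nothing extends them to the secondary models.

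**The concern.** The protocol supplies both links needed for confounding.

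- Predictor to covariate. On discounting, it says that "individuals with less education discount more than those with more education". On the CPT: "Individuals report the number of cigarettes they would smoke in a hypothetical day across a range of prices per cigarette". Some CPT measures, demand intensity above all, can be expected to overlap with a woman's actual cigarettes per day.
- Covariate to outcome. Under Treatment Conditions, smoking level and education are among the four stratification variables, chosen because they may influence maternal and child outcomes.

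Balancing the randomization on these variables does not help. It balances the arms, but k and the CPT measures are not randomized. A significant coefficient in the SAP model could mean only that heavier or less-educated smokers quit less often, and the trial would have no prespecified analysis to tell this apart from an effect of discounting or demand.

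**Working it through.** **The plan's own figure.** SAP, Sample Size gives power 0.80 at alpha 0.05 for odds ratios (ORs) of 2.0 to 2.5 per SD. This cannot be reproduced as written, because neither the event rate nor the predictor list is given. The usual approximation is

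detectable OR = exp{ √[ (z₀.₉₇₅ + z₀.₈₀)² / (N p(1−p)(1−R²)) ] },

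where R² is that of the predictor on the other covariates, which is not the total-model R² the SAP quotes. Inputs are N = 240, two-sided 0.05 (assumed; sidedness is not stated) and R² = 0.20 to 0.40.

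- Week 12, planned rates 15/35/35%, pooled p = 28.3%: OR 1.57 to 1.68.
- Week 24, rates 5/20/20% (both incentive arms assumed at 20%), pooled p = 15%: OR 1.76 to 1.92.

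Both lie below the stated range, so adjustment is affordable for a main-effect term. The figure has no other bearing on the point.

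**Simulation.**

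- From the documents: 80 per arm and the abstinence rates above.
- Assumed: a standard-normal covariate with an abstinence OR of 0.67 or 0.5 per SD, and a predictor with correlation ρ to it and no effect of its own.
- Test: the SAP model, taken as treatment, predictor and their interaction, against treatment alone. This is a 3-df likelihood-ratio test at 0.05.
- Replicates: 2,000 per scenario (1,971 to 1,989 usable at week 24 for the rows shown).

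Cells give the rejection rate without → with the covariate in the model. The last column is the mean OR per SD for the predictor in the unadjusted main-effect model.

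| ρ | Covariate OR | Week 12 | Week 24 | Predictor OR (wk 12 / wk 24) |
|---|---|---|---|---|
| 0.2 | 0.67 | 7.3% → 5.0% | 7.3% → 6.2% | 0.92 / 0.92 |
| 0.2 | 0.5 | 10.4% → 5.2% | 9.6% → 7.0% | 0.88 / 0.87 |
| 0.3 | 0.67 | 9.6% → 5.6% | 8.6% → 5.7% | 0.89 / 0.89 |
| 0.3 | 0.5 | 18.1% → 5.8% | 15.3% → 5.5% | 0.82 / 0.81 |
| 0.5 | 0.67 | 18.8% → 5.2% | 13.5% → 6.0% | 0.82 / 0.82 |
| 0.5 | 0.5 | 44.8% → 5.5% | 30.6% → 6.3% | 0.72 / 0.71 |

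At ρ = 0 the unadjusted rate is 5.3% to 5.6%. Extending ρ to 0.6 raises the top of the range, at week 12 with OR 0.5, to about 59% (separate runs gave 59% to 61%). A 1-df test of the predictor in a main-effect model is usually more exposed: 8% to 61% at week 12 and 7% to 45% at week 24 over the table's scenarios. With the covariate included it returns to 4.3% to 5.5%.

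For k and education, ρ of 0.2 to 0.3 in size and a covariate OR of 1.5 (= 1/0.67) correspond to the first and third rows: about 7% to 10%.

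**Events and model terms.** Week 24 events: 80 × 0.05 + 80 × 0.20 + 80 × 0.20 = 4 + 16 + 16 = 36. The SAP interaction model has 2 treatment + 1 predictor + 2 interaction = 5 terms. A main-effect model with education and cigarettes per day as single terms also has 2 + 1 + 2 = 5, or 36/5 = 7.2 events per term. Four covariates on top of the interaction model would make 9 terms, or 36/9 = 4 events per term.

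**The case against.** Several points on the other side stand.

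- **The SAP's wording is not exhaustive.** A reader might infer that it excludes covariates. It lists what the models will contain, does not say that nothing else may enter, and does not even list the predictor's main effect. The accurate statement is that the protocol's covariates were not carried over. That still leaves the set open to choice after the data are seen.
- **The hypothesis mentions treatment only.** The secondary aim expects discounting to predict abstinence at follow-up "assessments after controlling for the influence of treatment". For pure prediction, a k that works through education is a genuine predictor, and the unadjusted association is not false. The rates above are errors only if the claim is an independent effect. But the same aim also seeks to understand process, and Statistical Considerations ask for the covariates outright.
- **The power paragraph proves nothing here.** A reader might take "assuming total model R^2 ranging from 0.20 to 0.40" as evidence that a covariate-rich model was intended, since treatment alone gives a Nagelkerke R² of only about 0.08 to 0.09. The SAP model also contains the predictor and its interaction. With the predictor at the stated OR of 2.0 to 2.5, simulated R² is about 0.19 to 0.25, so the model reaches the lower part of the range without added covariates.
- **The large figures concern some CPT measures only.** Elasticity, which the protocol names for these models, is listed separately from intensity, and no passage ties it to cigarettes per day. Entry at 10 or more cigarettes per day also narrows that covariate's spread.
- **Over-adjustment is possible.** Where a CPT measure overlaps smoking level, adjustment may remove part of the construct under study. This argues for reporting both estimates.

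**Conclusion.** The point holds as an inconsistency between two current documents that limits what the secondary aim can claim. Followed as written, the SAP yields associations that may be carried partly or wholly by education or smoking level. They can support a marginal prediction statement, not a process interpretation.

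Direction and mechanism rest on the protocol's own text; the size does not. The 7% to 59% range depends on assumed correlations of 0.2 to 0.6 and covariate ORs of 0.67 to 0.5 per SD, none of which the documents give. It should not be quoted as this trial's false-positive rate. For discounting and education, the one predictor link the protocol states outright, the inflation is small under the modest assumptions used. It becomes large only if a CPT measure tracks cigarettes per day closely and smoking level strongly predicts quitting. The primary endpoint is unaffected.

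**What to change.** Amend SAP, Secondary Endpoint Analysis, to restore the protocol's adjustment:

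1. For each of log k and the CPT measures, fit as primary a logistic model with treatment condition, the predictor's main effect and a short, named set of baseline covariates, at least maternal education and cigarettes per day.
2. Fit the treatment interaction as an additional model, as the protocol has it.
3. Report both the covariate-adjusted and the treatment-only OR, and rest any process claim on the adjusted one.

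If leaving the covariates out was deliberate, the SAP should say so, give the reason, and confine its conclusions to prediction.

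The cost is a few sentences and no new data: both covariates are in the intake battery and in the SAP's randomization scheme. The downside is some extra terms with about 36 expected events at week 24, and a wider interval where demand overlaps cigarettes per day. The set should therefore stay small. With two single-term covariates the main-effect model has no more terms than the SAP's present interaction model.
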